Study protocol

Neonatologist-performed lung ultrasound during immediate transition after birth to predict the need for respiratory support persisting more than 1 hour – a pilot study

[name]

Department of Pediatrics, Division of Neonatology, Medical University of Graz,
[name]

[name], PhD

Department of Pediatrics, Division of Neonatology, Medical University of Graz,
[name]

[name], PhD

Department of Pediatrics, Division of Neonatology, Medical University of Graz,
[name]

Version 8.1

08.02.2024

1. Introduction

Lung ultrasound is an emerging clinical tool to assess the lung in a dynamic way. Recently, the focus has been on establishing lung ultrasound in the neonatal intensive care unit (NICU) as a point-of care application. As a result, the corresponding guidelines have been issued by the European Society of Paediatric and Neonatal Intensive Care (ESPNIC) in 2020. (Kurepa *et al.*, 2018; Singh *et al.*, 2020)

Neonatologist-performed lung ultrasound (NPLUS) has proven to be a safe, accessible, and reliable diagnostic tool in neonatal intensive care. Compared to X-ray examination, NPLUS is a highly specific and sensitive approach which is not relying on ionizing radiation (Aichhorn *et al.*, 2021; Singh *et al.*, 2021; Renz *et al.*, 2022).

Diagnostic applications for NPLUS include the evaluation and serial monitoring of respiratory conditions such as respiratory distress syndrome (RDS), transient tachypnoea of the newborn (TTN), pneumonia, pleural effusion, atelectasis, lung oedema, meconium aspiration syndrome (MAS) and pneumothorax. By applying the lung ultrasound score, a semi-quantitative method to assess the neonatal lung, neonatologists are able to identify infants in need for surfactant or infants at risk of bronchopulmonary dysplasia. (Rodriguez-Fanjul *et al.*, 2020; Aichhorn *et al.*, 2021; Küng *et al.*, 2022; Schmidt and Ramamoorthy, 2022)

2. Background

Lung ultrasound is based on the interpretation of ultrasound artefacts (A- and B- lines), analysis of the pleura, and the visualization of consolidations and pleural effusions enhancing the differential diagnosis of acute respiratory distress in newborns. The impairment of lung aeration can be quantified based on the number and type of visualized artefacts. (Raimondi *et al.*, 2021; Ollier *et al.*, 2022)

There is emerging evidence that NPLUS is a reliable tool to differentiate between the different causes leading to RDS in neonates. By today, different scoring systems have been developed in different clinical contexts. (Brat *et al.*, 2015; Mongodi *et al.*, 2021; Rodriguez-Gonzalez *et al.*, 2022) These scores aim at giving a comprehensive look on the lung's condition by screening the lung fields.

Despite the growing body of evidence, studies on NPLUS during stabilization and resuscitation immediately after birth are still scarce. In the study performed by Blank *et al.*, they found that in healthy term and late preterm infants within the first 20 min after birth, the lung ultrasound score for neonates requiring respiratory support at the NICU was highly predictive. (Blank *et al.*, 2017) In the ULTRASURF study, a randomized controlled trial from Rodriguez-Fanjul *et al.* in 2020, NPLUS was performed within 1 hour after birth in preterm neonates (≤ 32 weeks of gestation) with RDS. In the study protocol, three scans of the anterior, lateral, and posterior chest walls were performed on each side. A 0- to 3-point score was given for each scanned area with a total score ranging from 0 to 18. One randomized group received surfactant based on this lung ultrasound score ≥ 8 and FiO₂ thresholds, in the other group surfactant was administered solely based on FiO₂ thresholds. In the group, in which the diagnosis was based on the lung ultrasound score, neonates received earlier surfactant without increasing the number of patients requiring surfactant treatment. (Rodriguez-Fanjul *et al.*, 2020)

Neonates born by a Caesarean section are particularly prone to have an altered adaption to extrauterine life. Especially in the first hours after birth, TTN may occur due to delayed lung fluid clearance after birth. (Riskin *et al.*, 2005; Poerio *et al.*, 2021) While acute RDS in the first hours after

birth may be a self-limiting disorder and therefore a benign condition, it remains difficult to identify infants in need for further respiratory support at the NICU. Admission to the NICU not only causes parental stress but also contributes to additional healthcare costs. (Pierro *et al.*, 2023). Using the lung ultrasound score for the early identification of neonates in need of respiratory support persisting more than 1 hour would be highly advantageous. Neonates requiring further treatment could benefit from early admission at the NICU, whilst the others could be prevented from an ‘unnecessary’ transfer to the NICU which would in turn reduce the burden of transport, workload, and healthcare costs.

3. Objectives

The objective of this study is to evaluate the role of NPLUS during the immediate transition after birth of late preterm and full-term neonates using the lung ultrasound score to predict the need for respiratory support persisting more than 1 hour. NPLUS will be conducted at specific time points after birth (at 5, 15, 30 and 60 minutes) by a trained medical doctor who will complement as an additional member of the medical team.

- **Hypothesis I:**

We hypothesize that there is a cut-off value of the lung ultrasound score performed 5, 15, 30 and 60 minutes after birth that is reliable to predict the need for respiratory support persisting > 1 hour in late preterm and full-term neonates.

- **Hypothesis II:**

We hypothesize that there is a cut-off value of the lung ultrasound score performed 5, 15, 30 and 60 minutes after birth that is reliable to predict the need for admission to the NICU in late preterm and full-term neonates.

- **Hypothesis III:**

We hypothesize that neonates in need of respiratory support persisting > 1 hour have significantly higher lung ultrasound scores even when assessed already in 5, 15, 30 and 60 minutes after birth, compared to neonates requiring respiratory support < 1 hour after birth.

- **Hypothesis IV:**

We hypothesize that there is a correlation between the lung ultrasound score performed at 5, 15, 30, and 60 minutes after birth, the length of respiratory support and the required mode of ventilation.

- **Hypothesis V:**

We hypothesize that the lung ultrasound score assessed by NPLUS decreases between 5 and 60 minutes after birth.

4. Design, setting and participants

The present **study design** is conceived as an observational prospective pilot study.

Study procedures: In this study NPLUS is performed to quantify the lung ultrasound score 5, 15, 30 and 60 minutes after birth in late preterm and full-term neonates. The lung ultrasound examination of the anterior and lateral chest walls is conducted in supine position of the neonate, the examination of the posterior chest walls requires turning the neonate into lateral position for a couple of seconds. After 60 minutes after birth, the study patients do not require any additional examination. Furthermore, we ensure that the clinical routine care is not affected by NPLUS.

Routine care: Immediately after cord clamping, the neonate is placed under an overhead heater on the resuscitation cot ('CosyCot', Fisher&Paykel Healthcare; New Zealand) in supine position by the midwife. If obstructions of the upper airways are obvious, immediate suction of the oropharynx is performed. If necessary, respiratory support is applied by using a 'Neopuff Infant T- Piece Resuscitator' (Perivent, Fisher& Paykel Healthcare; New Zealand) and a face mask of appropriate size (PVC face mask no. 0 or 1, VBM; Germany). For infants with RDS, NPLUS is an optional diagnostic approach to evaluate lung aeration during neonatal transition and to rule out morbidities such as a pneumothorax.

NPLUS is frequently performed in daily routine within the first 30 minutes after birth for an early examination of the lungs and/ or following the initial treatment after one to two hours after birth when the neonate is admitted to the NICU.

Lung ultrasound score: Although the score of Brat *et. al.* is currently the most used one, we intend to use the score introduced by Rodriguez-Fanjul *et al.* in the ULTRASURF study. (Brat *et al.*, 2015; Rodriguez-Fanjul *et al.*, 2020) This score was developed to assess the neonate's lung within the first hour after birth, focusing not only on the anterior and lateral parts of the hemithorax but it also considers the posterior chest walls. Since our study is particularly aimed at neonates born by a Caesarean section, for which TTN is likely to occur, it is advantageous to include the posterior chest walls in the lung ultrasound score. (Riskin *et al.*, 2005; Blank *et al.*, 2017) Moreover, a congenital pneumonia is detected the best in a comprehensive examination of the lung.

NPLUS is conducted with a 12-15 MHz linear transducer preferably using the presets "lung" or "small parts". Sequences of 3-5 seconds are saved and scored. To minimize interference with the routine care, NPLUS will be performed by an independent trained medical doctor and clinical findings will not be passed on to the medical team in charge. The only exception to communicate the obtained NPLUS findings would be a pneumothorax. In this situation the diagnosis will be communicated to the medical team, and the neonate will be excluded from the study.

To ensure **inter-observer reliability** the anonymous video sequences are then blinded and rated by two independent neonatologists.

Inclusion criteria:

- Late preterm neonates (born between 34 0/7 and 36 6/7 weeks of gestation) and full-term neonates (born later than 36 6/7 weeks of gestation) delivered by Caesarean section at the Department of Obstetrics and Gynaecology, Medical University of Graz
- Presence of any sign of respiratory distress (defined as tachypnoea/ dyspnoea, grunting, flaring of the nostrils or chest retractions)
- Written informed consent obtained from the parents prior to birth.

Exclusion criteria:

- Presence of cardiopulmonary malformations
- Patients with pneumothorax diagnosed by NPLUS

Sample size: Statistical analysis for cut-off determination will be performed with a sample-size of 40 individuals, excluding patients with pneumothorax diagnosed by NPLUS. Hence, we aim at comparing 20 neonates who are transferred to the NICU with 20 neonates who initially need respiratory support but then do not require any 60 minutes after birth.

Sample size calculations cannot be performed beforehand, since no data from previous studies are available. Hence, this pilot study is conducted to generate data for the sample size calculation of the consecutive main study (Thabane *et al.*, 2010).

5. Statistical analysis

Demographic information, clinical characteristics, and lung ultrasound features will be summarized. First, the Kolmogorov–Smirnov test will be applied to test the data significance, which will then be represented as the mean (standard deviation, SD) or median (interquartile range, IQR). The predictive performance of the lung ultrasound score for the need for respiratory support persisting more than 1 hour after birth and for admission to the NICU will be analysed by plotting the receiver operating characteristic (ROC) curve, and areas under the ROC curves (AUCs) determining cut-off values. Group differences in primary and secondary outcome parameters between patients who are transferred to the NICU in need for respiratory support for more than 60 minutes and patients who do not need any respiratory support after 60 minutes after birth are calculated using χ^2 and Fisher's exact tests for discrete variables, and t-test or Mann-Whitney U test for continuous variables. Additionally, the correlations between the lung ultrasound score, length of respiratory support and the mode of ventilation will be analysed using either the Spearman's rank correlation coefficient or the Pearson's correlation depending on which one is more appropriate. The correlation analyses are considered in an explorative sense; therefore, no multiple testing corrections will be performed. SPSS23.0 (IBM Corporation, New York, NY, USA) is used for statistical analysis.

6. Outcome measures

Primary

- Determination of the lung ultrasound score according to Rodriguez-Fanjul *et al.* 2020 at 5, 15, 30 and 60 minutes after birth
- Need for respiratory support persisting more than 1 hour
- Admission to the NICU

Secondary

- Length of respiratory support (in minutes)
- Mode of respiratory support (non-invasive versus invasive ventilation)
- Routinely obtained capillary blood gas analysis of the newborn
- Routinely obtained monitoring parameters including arterial oxygen saturation (SpO₂), heart rate (either by pulse oximetry or electrocardiography), and cerebral oxygen saturation (near-infrared spectroscopy)
- SpO₂/FiO₂ ratio (S/F ratio)
- pH of the umbilical artery
- Apgar score
- Pregnancy risk factors including intra-amniotic infection, and premature rupture of the membranes
- Prenatal corticosteroids

7. Research plan and time table

The study will start in spring 2024.

The study is designed for an approximate running time of three years.

8. References

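### For Hypothesis I the 60-minute score is called a predictor of support beyond 1 hour, but counted from birth it has no lead time over that outcome

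*Combined protocol and SAP*

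**What the plan says.** Section 3 (Objectives), Hypothesis I, names four scan times in one phrase. It expects a cut-off for a "lung ultrasound score performed 5, 15, 30 and 60 minutes after birth that is reliable to predict the need for respiratory support persisting" for more than 1 hour. Hypothesis III uses the same four times for a group comparison: scores are to be higher in infants with longer support "even when assessed already in 5, 15, 30 and 60 minutes after birth, compared to neonates requiring respiratory support" for less than 1 hour, there counted from birth.

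The purpose is given at the end of section 2 (Background): "Using the lung ultrasound score for the early identification of neonates in need of respiratory support persisting more than 1 hour" is described as highly advantageous, because it could bring early admission for some infants and spare others a transfer.

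The groups are described in section 4, Sample size. One is "20 neonates who are transferred to the NICU"; the other is "20 neonates who initially need respiratory support but then do not require any 60 minutes after birth". Section 5 (Statistical analysis) plans ROC curves, AUCs and cut-off values under the label of predictive performance, with the hour of support counted from birth. Its non-case group is also counted from birth. Its case group needs NICU transfer plus support for more than 60 minutes, with no starting point given. The primary outcome line in section 6 gives more than 1 hour, again without a starting point.

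No section treats the 60-minute scan differently from the three earlier ones.

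**The concern.** A predictor has to be available before the outcome it predicts is known. If the hour is counted from birth, the last scan is taken at the moment the threshold is reached. The team can then already see whether the infant is on support. A cut-off derived from that scan describes how the score relates to present status. It cannot identify the infant early, however high its AUC.

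Followed as written, the plan would report this result beside the three earlier ones under the same heading of predictive performance. Section 5 names no primary time point and gives no rule for separating a concurrent estimate from a predictive one. What is at stake is how one of the four Hypothesis I results is interpreted. The conduct of the study is not at stake: findings other than pneumothorax are withheld from the treating team (section 4), so care is unaffected.

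**Working it through.** The plan states no lead time, so there is no figure of its own to reproduce. The lead times follow from its definitions.

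**Inputs.** Scan times t = 5, 15, 30 and 60 minutes after birth (section 3, Hypothesis I). Outcome threshold: 60 minutes. Start of the outcome clock: birth in the four places below, unstated elsewhere.

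| Place | Clock for the hour |
|---|---|
| Section 3, Hypothesis III comparator | birth |
| Section 4, Sample size, non-case group | birth |
| Section 5, ROC sentence | birth |
| Section 5, non-case group | birth |
| Section 3, Hypothesis I | not stated |
| Section 5, case group | not stated |
| Section 6, primary outcome line | not stated |

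**Birth clock.** Lead = 60 − t.

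- 5-minute scan: 60 − 5 = 55 minutes (55/60 = 92% of the hour)
- 15-minute scan: 60 − 15 = 45 minutes (75%)
- 30-minute scan: 60 − 30 = 30 minutes (50%)
- 60-minute scan: 60 − 60 = 0 minutes (0%)

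**Duration clock.** If the hour runs from the start of support, s minutes after birth, then lead = s + 60 − t. The documents do not give s. As an assumption, take s from 0 to 15 minutes.

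- 5-minute scan: 55 to 70 minutes
- 15-minute scan: 45 to 60 minutes
- 30-minute scan: 30 to 45 minutes
- 60-minute scan: 0 to 15 minutes (0/60 to 15/60, or 0% to 25% of the hour)

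For the 60-minute scan the formula reduces to lead = s, so the lead is simply the delay before support began.

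**Comparison that does not depend on s.** The lead at 30 minutes minus the lead at 60 minutes is (s + 30) − s = 30 minutes, for any s and on either clock. The 60-minute scan would have a 30-minute lead only on the duration clock and only if s = 30.

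**Share affected.** Reading Hypothesis I as one cut-off per scan time, 1 of 4 is affected.

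**What cannot be computed.** The documents give no score distribution, no expected AUC and no rate at which support is restarted or stopped after 60 minutes. Any change in the AUC from using a concurrent scan is therefore not derivable.

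**The case against.** The strongest reply is that the outcome is not simply support status at minute 60. In section 4 the case group is defined by NICU transfer, and in section 5 by transfer together with support. No time is set for the transfer. Section 4, Routine care, describes scans "following the initial treatment after one to two hours after birth when the neonate is admitted to the NICU", which suggests that admission can follow the 60-minute scan. Support could also be restarted later. This stands: some infants could still change group, so status at 60 minutes is largely known but not fixed. It does not give the scan lead time over the support threshold itself.

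A second reply is that the hour may mean duration of support. That reading is open where no clock is named, and the delay to the start of support could be longer than a few minutes, because the inclusion criteria set no time by which distress must appear. The range of 0 to 15 minutes is only an illustration. The 30-minute shortfall against the preceding scan holds whatever the delay.

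A third reply is that this is a pilot, that a reader would see the 60-minute scan set against a 1-hour outcome, and that the remedy is mainly a label. This limits the weight. It does not remove the point, because the label in the plan is the wrong one for this scan.

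Four stronger readings are tempting and are not supported:

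- **The 60-minute AUC is inflated or circular.** The score is a separate measurement from support status, and the documents give nothing from which to derive an effect on the AUC.
- **The main study would be wrongly sized.** Section 4 says that "this pilot study is conducted to generate data for the sample size calculation of the consecutive main study", but nowhere that the 60-minute AUC will be the input.
- **The 60-minute comparison under Hypothesis III fails too.** A difference in scores between groups needs no lead time, so the planned test stands.
- **The 60-minute scan should be dropped.** It remains useful for NICU admission (II), correlation with length and mode of support (IV) and change over time (V).

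**Conclusion.** The point holds for the 60-minute score as a predictor of support beyond 1 hour under Hypothesis I. On the birth clock, which the ROC sentence itself uses, its lead time is 0 minutes, against 55, 45 and 30 minutes for the earlier scans. The resulting cut-off is largely a concurrent classification and cannot serve the purpose stated in section 2.

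The birth-clock figures rest on the documents alone. The duration-clock range rests on an assumed start of support. The word largely is needed because NICU transfer has no set time and support status may change after the scan.

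The weight is minor to moderate: one of four time points in an observational pilot, with the 5-, 15- and 30-minute scans not in question and no derivable effect on the AUC or on main-study sizing. It is worth correcting because it changes what may be concluded from one result, at almost no cost.

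**What to change.** In Hypothesis I, section 5 and the primary outcome line of section 6, state that more than 1 hour is counted from birth, as the ROC sentence already says. Then separate the last scan in the ROC analysis of this outcome. Suggested text for section 5:

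*Support persisting more than 1 hour is counted from birth. Predictive AUCs and cut-offs for this outcome use the 5-, 15- and 30-minute scores. The 60-minute score coincides with the outcome threshold; its AUC for this outcome is reported as a concurrent association and not as predictive performance.*

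Keep the 60-minute scan, the planned Hypothesis III group test at 60 minutes, and Hypotheses II, IV and V as they are.

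The cost is wording in three places. No scan, infant or data item is added or removed, and the 60-minute AUC is still calculated. The one loss is that it can no longer be reported as prediction of support beyond 1 hour. The change does not settle the timing of NICU transfer in the case definition, which stays open.

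### Could the treating team's own early lung ultrasound undermine the outcomes that the study score is meant to predict?

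*Combined protocol and SAP*

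**What the plan says.** Section 3 (Objectives) has the study scans done "by a trained medical doctor who will complement as an additional member of the medical team".

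Section 4 describes the study as observational. Its Study procedures paragraph ends with the assurance that "we ensure that the clinical routine care is not affected by NPLUS". The Routine care paragraphs that follow include ultrasound in that care: "For infants with RDS, NPLUS is an optional diagnostic approach to evaluate lung aeration during neonatal transition". They add that "NPLUS is frequently performed in daily routine within the first 30 minutes after birth for an early examination of the lungs", and/or one to two hours after birth, at NICU admission.

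The part of section 4 on the lung ultrasound score sets the withholding rule: "NPLUS will be performed by an independent trained medical doctor and clinical findings will not be passed on to the medical team in charge". It allows one departure: "The only exception to communicate the obtained NPLUS findings would be a pneumothorax". The matching exclusion criterion reads "Patients with pneumothorax diagnosed by NPLUS".

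Section 6 (Outcome measures) names the study score at the four time points. It also lists some routine data, namely blood gas and monitoring values, but no routine ultrasound. The Sample size paragraph gives the pilot's purpose: "this pilot study is conducted to generate data for the sample size calculation of the consecutive main study".

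**The concern.** A prediction study is easiest to interpret when the people who determine the outcome have not seen the predictor. Support beyond one hour and NICU admission are both decided by the treating team, and the protocol takes care to keep the study findings from that team. Yet it also says that the team's own practice often includes the same examination in the first half hour, a window that overlaps the 5, 15 and 30 minute study scans. Enrolled infants must show respiratory distress, so they resemble the infants for whom the site describes this practice.

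One abbreviation, NPLUS, covers both study and routine scans. A reader could therefore ask whether routine scanning goes on alongside the study, or whether all early scanning passes to the study doctor and is withheld.

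If routine scans go on and are seen before the decision, the AUC and cut-off might partly reflect clinicians acting on similar images. Those estimates may inform the main study, and the minute at which a clinician saw a scan is hard to recover later.

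**Working it through.** The question is mainly one of text, so the relevant statements are compared first. Arithmetic comes in only when asking what a remedy would buy.

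**1. Does routine scanning continue?**

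| Statement in the protocol | Routine scans continue, only study scans withheld | All early scans done by the study doctor and withheld |
|---|---|---|
| Observational design (section 4) | fits | sits badly: the study would remove a diagnostic option |
| Routine care not affected (Study procedures) | fits | contradicts it |
| Ultrasound described within routine care | fits | contradicts it, given the row above |
| Study doctor is an additional person (section 3) | fits: added, not substituted | possible, but not stated |
| Independent doctor used so as to disturb care as little as possible | fits | sits badly |
| Exception limited to findings obtained by NPLUS | fits, read as the study's own scans | fits |

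No row favours the right-hand column, and two contradict it. Continuation is an inference, but the only one that leaves the section consistent.

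**2. Does the shared abbreviation change who is analysed?** Under the exclusion criterion, an infant with a pneumothorax found by ultrasound leaves the study whichever doctor held the probe. The ambiguity does not affect the analysis set.

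**3. Which routine scans could matter?** The protocol gives two windows, joined by and/or. The later one, at one to two hours and tied to NICU admission, comes too late for the 60-minute status and accompanies admission rather than preceding it. Only the first 30 minutes is relevant to the primary outcomes. For that window the sole measure is an adverb describing general practice. Nothing states how many enrolled infants would be scanned, or that a scan decides support or admission.

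**4. Does section 6 show that the scans go unrecorded?** Section 6 lists outcome measures and does not claim to list every item collected. Section 5 promises summaries of demographic data, yet section 6 has no item for sex or birth weight. Absence from section 6 therefore says little about what is recorded, and the case report form is not among the documents.

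**5. What would a record of routine scans add?** Inputs: 20 infants per group (Sample size paragraph); the AUC values are assumptions.

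Precision of the AUC, by the Hanley-McNeil formula, with A the AUC, Q₁ = A/(2 − A) and Q₂ = 2A²/(1 + A):

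Var = [A(1 − A) + 19(Q₁ − A²) + 19(Q₂ − A²)] / 400

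- A = 0.70: [0.210 + 19(0.0485) + 19(0.0865)]/400 = 0.00693; SE 0.083; half-width 1.96 × 0.083 = 0.16
- A = 0.80: [0.160 + 19(0.0267) + 19(0.0711)]/400 = 0.00504; SE 0.071; half-width 0.14
- A = 0.90: [0.090 + 19(0.0082) + 19(0.0426)]/400 = 0.00264; SE 0.051; half-width 0.10

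Share scanned in one group, exact (Clopper-Pearson) 95% limits:

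- 0 of 20: 0 to 1 − 0.025^(1/20) = 17%
- 5 of 20: 9% to 49%
- 10 of 20: 27% to 73%
- 16 of 20: 56% to 94%

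Comparing the shares between groups by Fisher's exact test, two-sided 5%: power is 41% for true shares of 80% versus 50%, and 16% for 70% versus 50%.

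Even a clear difference in shares would not show bias, because sicker infants may simply be scanned more often. Restricting the ROC analysis to unscanned infants would shrink groups of 20 further and select on severity.

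**The case for a change.** The strongest case for acting is that the inference in favour of continuation makes the problem more real. If routine scans do go on, the team may see the same kind of information that the withholding rule keeps from it, and that rule then gives only partial protection. A clarifying sentence and one form item would cost almost nothing. If no infant turned out to have been scanned, the worry would vanish for this sample. The later routine scan could also bear on length of support, which Hypothesis IV correlates with the score.

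Part of this stands. No sentence states the position outright, the pathway is plausible, and explicit wording would be tidier. Wide confidence intervals do not excuse a bias either, since imprecision and bias are separate faults.

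What does not stand is the step from there to a defect in the plan. No stated rule gives a wrong result. The proposed record could describe exposure but could not test or correct for influence, so the AUC, the cut-off and every planned analysis would stay as they are. The one measure that would remove the pathway, stopping routine scans, would interfere with care that the study has undertaken to leave alone. The length-of-support correlation is declared exploratory in section 5.

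**Conclusion.** No change to the plan follows. This is a gap in wording that the surrounding text fills sensibly: optional ultrasound belongs to routine care, routine care is left alone, and the withholding rule applies to the study's own scans. Accepting that treating clinicians may use their usual tools is a fair trade-off in an observational pilot.

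The size and direction of any effect on the AUC or cut-off cannot be derived from the documents. A figure would need assumed values for how many infants are scanned, how many scans are seen before the decision, and how much they sway it. The result would only return those assumptions.

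The conclusion rests on two things: reading the routine-care assurance together with the description of that care, and the absence of any stated rule that makes support or admission depend on ultrasound. If such a rule existed locally, the point would carry more weight. As the documents stand, those reporting the pilot can note among its limitations that the treating team may have had its own ultrasound findings, and that needs no amendment.

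### Pneumothorax is the only study-scan finding that may be communicated, so as written the operator cannot report any other finding judged to need immediate treatment (minor safety gap)

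*Combined protocol and SAP*

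**What the plan says.** The rule is in Section 4 (Design, setting and participants), in the paragraph on how the scan is performed. An independent trained doctor scans the infant, and "clinical findings will not be passed on to the medical team in charge". The stated purpose is to keep the study from interfering with routine care. The next sentence reads: "The only exception to communicate the obtained NPLUS findings would be a pneumothorax". A pneumothorax is reported to the team and the infant leaves the study.

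Other statements bear on the rule:

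- Section 3 (Objectives) describes the operator as "a trained medical doctor who will complement as an additional member of the medical team".
- Section 4, on inter-observer reliability: "the anonymous video sequences are then blinded and rated by two independent neonatologists".
- Section 4, Study procedures: "After 60 minutes after birth, the study patients do not require any additional examination".
- Section 4, Routine care, on infants with respiratory distress syndrome: "NPLUS is an optional diagnostic approach to evaluate lung aeration during neonatal transition". It adds: "NPLUS is frequently performed in daily routine within the first 30 minutes after birth for an early examination of the lungs". The same sentence gives a scan one to two hours after birth, at NICU admission, as an addition or alternative.
- Section 6 (Outcome measures) lists oxygen saturation, heart rate and cerebral oxygenation as routinely monitored. It names respiratory support beyond one hour and NICU admission as primary outcomes.

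**The concern.** A rule with a single named exception leaves no room for judgement. Infants enter the study because they show respiratory distress, and the protocol itself says that lung ultrasound can show more than pneumothorax. If the operator sees something else that in their judgement needs treatment at once, the study holds information that the treating team does not have. The operator must then either stay silent or deviate from the protocol. What is at stake is the safety of an individual newborn.

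The blinding itself is right. The treating team decides on respiratory support and NICU admission. Telling it the score would let the test influence the outcomes that it is meant to predict.

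**Working it through.** The plan states no figure on this point, so the check sets the text side by side.

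1. **Scope of the rule.** It covers the clinical findings of the study scan in general, not just the score.
2. **Scope of the exception.** The word *only* closes the list at one item.
3. **Other routes of release.** None was found. Section 4 promises that routine care will not be affected by the study scan, which guards against interference and authorises no disclosure. The description of the operator in Section 3 makes silence in an emergency less likely but grants no permission. Cardiopulmonary malformations are an exclusion criterion, yet nothing says that one seen on the study scan is to be reported. Sections 5 and 6 do not address the matter.
4. **Can the scan show something else?** Yes. Section 1 names meconium aspiration, lung oedema, atelectasis, effusion and pneumonia among the conditions that lung ultrasound can evaluate. Section 4 gives congenital pneumonia as one reason for a comprehensive scan. Neither section says that any of these needs urgent treatment on the scan alone.
5. **Who could speak in time?** Apparently only the operator at the cot. The two raters see anonymous, blinded clips after the event, and the study plans no later examination. This is inferred from the order of events; the protocol gives no time for the rating.
6. **What reduces the risk?** The treating team's own assessment, routine monitoring, and clinical ultrasound where the team chooses it. The planned comparison group also consists of "20 neonates who initially need respiratory support but then do not require any 60 minutes after birth". None of this releases a study-scan finding. Because clinical ultrasound is optional and may come only at NICU admission, an early clinical scan is not assured.

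**Frequency.** The documents give none, so p, the chance of such a finding per infant, is assumed. Expected number = n × p; chance of at least one = 1 − (1 − p)^n. The protocol's 40 is the analysed set, counted after pneumothorax exclusions, so more infants may be scanned. An assumed 60 is shown beside it.

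| Assumed p | Expected, n = 40 | At least one, n = 40 | Expected, n = 60 | At least one, n = 60 |
|---|---|---|---|---|
| 0.1% | 0.04 | 3.9% | 0.06 | 5.8% |
| 0.5% | 0.2 | 18.2% | 0.3 | 26.0% |
| 1% | 0.4 | 33.1% | 0.6 | 45.3% |
| 2% | 0.8 | 55.4% | 1.2 | 70.2% |

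For example, 1 − 0.99^40 = 0.331 and 1 − 0.99^60 = 0.453. These illustrate a range of assumptions and neither estimate nor bound the risk. The treating team may already know of some of these findings, which pulls the safety gap down; a larger number scanned pushes it up.

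**The case against.** The best defence is that the rule is deliberate and easy to audit. Pneumothorax, the one morbidity that the Routine care paragraph gives as an example to rule out, is already released. A wider clause rests on the operator's judgement and has no listed criteria. The likely candidates also impair aeration, which the score measures, so disclosures would tend to fall on infants with high scores. This stands as a reason to keep the clause narrow and to record each use. It does not justify a rule that forbids the operator to speak at all.

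It is also fair to say that no harm is shown. Section 1 lists conditions for evaluation and serial monitoring, not emergencies. Consent pages are not among the documents reviewed, so any wording there on incidental findings could not be checked. Both points limit the weight of the concern without removing the gap in the text.

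A reader might infer three stronger things:

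- **That the protocol knowingly withholds life-threatening findings, or that infants will be harmed.** It contains no such instruction. The result follows from a general rule with one exception, and no urgent condition is identified.
- **That the blinding should be dropped.** The outcomes depend on the treating team's decisions, so ordinary findings should stay undisclosed.
- **That a disclosed infant would distort the accuracy results enough to need a second ROC analysis.** With 20 per group, an assumed sensitivity of 16/20 has an exact 95% interval of about 56% to 94%. One infant is negligible beside that width.

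**Conclusion.** The point holds as a low-frequency safety gap of minor severity. The text is clear: one exception, and no override anywhere in the documents. Its practical size is unknown, since it depends on how often a finding other than pneumothorax would be judged to need immediate treatment and would not already be known to the treating team. The documents inform neither. The conclusion rests on reading the rule as written; a doctor at the cot might well speak up anyway, but the protocol should not make that a deviation. The planned analysis is not called into question.

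**What to change.** Reword the exception in Section 4 so that it covers *a pneumothorax or any other finding that the operator judges to need immediate treatment*. State that the lung ultrasound score and non-urgent aeration findings remain undisclosed. Log each disclosure with its time and the finding. By default, handle such an infant as a pneumothorax case is handled now: tell the team, exclude the infant, and report how many were excluded for this reason. No additional analysis is needed.

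The cost is a one-sentence amendment with a short statement on handling, and an entry in the case report form. The downsides are that the treating team is occasionally unblinded and that a few infants are lost from the analysed set. Excluding infants on the basis of the scan is a form of selection, but the plan already accepts it for pneumothorax, and reporting the number keeps it visible.
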